9.5.3 Post-Stent Placement Assessments

• Venography to assess post-procedural target vessel lumen diameter and to determine residual target lesion stenosis. This assessment will serve as the baseline for determining the primary efficacy

STE-HUM-007P US Clinical Protocol Revision C

Confidential

Page 28 of 70

endpoint at the 12 month follow-up (or prior Interval Evaluation, when applicable). When venographic data is available at the 12 month visit, values from the venogram obtained at the Post-Stent Placement will serve as the subject's baseline.

- Adverse event assessment
- Extended Anticoagulation Protocol (See Appendix 2.) Anticoagulation or antiplatelet treatment for concomitant conditions should be continued at the discretion of the enrolling physician. Study patients should also receive anticoagulation or antiplatelet therapy, per the following guidelines. These guidelines apply through the 12 month visit.
 - Patients on extended Vitamin K antagonists or direct thrombin or Factor Xa inhibitors prior to enrollment should continue on warfarin post-procedure with a target INR of 2-3, or within the documented therapeutic range for INR per local guidelines.
 - Patients with a history of ≥2 thrombo-embolic event(s) and not on extended Vitamin K antagonists or direct thrombin or Factor Xa inhibitors prior to enrollment will be anticoagulated following the procedure and continue through the 12 month visit, as per ACCP guidelines⁷ (Vitamin K antagonists such as warfarin to achieve an INR of 2-3 [or an INR within the documented therapeutic range for INR per local guidelines] or direct thrombin or Factor Xa inhibitors such as rivaroxaban per recommended dosing).
 - Patients with a history of <2 prior thrombo-embolic event OR patients with no history, but where the obstruction is determined to be caused by previous silent thrombotic event, will begin anticoagulation post-procedure and continue for 6 months in the case of non-occlusive obstruction (Vitamin K antagonists such as warfarin to achieve an INR of 2-3 [or an INR within the documented therapeutic range for INR per local guidelines], or direct thrombin or Factor Xa inhibitors such as rivaroxaban per recommended dosing). From 6 months through the 12 month visit, these patients should receive low-dose ASA.

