 - Patients with occlusive obstruction should receive Vitamin K antagonists such as warfarin to achieve an INR of 2-3 (or an INR within the documented therapeutic range for INR per local guidelines), or direct thrombin or Factor Xa inhibitors such as rivaroxaban per recommended dosing through the 12 month visit.
 - Patients who were on clopidogrel or prasugrel pre-procedure will resume their baseline dose within 24 hours of the procedure and continue as required for the underlying condition UNLESS the enrolling physician believes that the

STE-HUM-007P US Clinical Protocol Revision C

Page 29 of 70

need for anticoagulation outweighs the need for anti-platelet drugs.

- All patients not receiving anticoagulation therapy or antiplatelet therapy as noted above will receive low-dose ASA (i.e. 75 mg, 81mg, etc.) daily throughout the 12 month visit.
- IVUS to assess stent characteristics (apposition, webbing, coverage of target lesion, etc.)
- Physician evaluation of technical difficulty of implantation

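### Section 9.5.3 tells patients already on a direct thrombin or Factor Xa inhibitor to continue warfarin, which they are not taking; a second rule, for fewer than two prior events, is ambiguous about patients with none

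*Combined protocol and SAP*

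**What the plan says.** Section 9.5.3 lists six antithrombotic rules for the period after stenting and says of them: "These guidelines apply through the 12 month visit". They are numbered here in the order in which they appear.

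- **Rule 1** is for patients anticoagulated before enrollment. It joins users of Vitamin K antagonists with users of "direct thrombin or Factor Xa inhibitors prior to enrollment should continue on warfarin post-procedure with a target INR of 2-3", or within a locally documented INR range.
- **Rule 2** is for patients with two or more prior events "and not on extended Vitamin K antagonists or direct thrombin or Factor Xa inhibitors prior to enrollment will be anticoagulated", with a drug of either class.
- **Rule 3** opens "Patients with a history of <2 prior thrombo-embolic event OR patients with no history, but where the obstruction is determined to be caused by" a silent thrombotic event. These patients "will begin anticoagulation post-procedure and continue for 6 months in the case of non-occlusive obstruction", again with either class. It then adds: "From 6 months through the 12 month visit, these patients should receive low-dose ASA".
- **Rule 4** is for occlusive obstruction: either class, through the 12-month visit.
- **Rule 5** is for patients on clopidogrel or prasugrel beforehand, who resume it unless the physician judges the need for anticoagulation to be greater.
- **Rule 6** takes the remainder: "All patients not receiving anticoagulation therapy or antiplatelet therapy as noted above will receive low-dose ASA".

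The section also points to Appendix 2. Only the heading of that appendix is visible in the text available for this review.

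**The concern.** Rule 1 names one drug for a group that, by its own description, includes patients taking other drugs. The rest of the protocol keeps the classes apart: the baseline laboratory list in Section 9.3 names them separately, and rules 2 to 4 offer either one. Rule 3 sets a threshold that includes zero if taken numerically, and then adds a condition for patients with no history that would be unnecessary if they were already covered.

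Both points bear on how patients are treated for a year. Thrombosis of the stented segment is a patency failure (Section 15.8.1). Bleeding, DVT outside the target vein and pulmonary embolism all appear, with qualifying conditions, in the 30-day safety composite (Section 11.1.4). The trial has one arm, up to 45 centers and fixed performance goals, so no concurrent control would share any difference in site practice. Trial success also requires observed patency above 0.855 in the non-thrombotic group by itself (Section 15.7), and that is the group most exposed to the rule 3 ambiguity. Sites review anticoagulation against this protocol at discharge and at 1, 6 and 12 months. Compliance cannot be judged consistently against a rule that has two readings.

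**Working it through.** The plan gives no figure on this point, so there is nothing to reproduce. The check sets the rules side by side.

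| Rule | Patients covered | Agent named | Period |
|---|---|---|---|
| 1 | On a Vitamin K antagonist or direct inhibitor before enrollment | Warfarin, INR target | Through 12 months |
| 2 | Two or more events, not on those agents | Either class | Through 12 months |
| 3 | Fewer than two events, or no history with a silent event as cause; non-occlusive | Either class | 6 months, then ASA to 12 months |
| 4 | Occlusive obstruction | Either class | Through 12 months |
| 6 | Not covered above | ASA | Through 12 months |

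**Rule 1.** For a patient on warfarin, the verb and the drug agree. For a patient on a direct inhibitor they cannot both hold. If the site follows the verb, the patient stays on the current agent and the INR target has nothing to apply to. If the site follows the drug name, the patient is switched and nothing has been continued. The other rules do not settle it:

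- Rule 2 excludes these patients by its own terms.
- Rule 3 speaks of beginning anticoagulation.
- Rule 4 applies only to occlusive disease and accepts either class, so it is compatible with both readings of rule 1.

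**Rule 3.** Classify patients by prior anticoagulant (none, Vitamin K antagonist, direct inhibitor), by history (no events and no silent thrombosis, no events but silent thrombosis, one event, two or more) and by occlusive or non-occlusive obstruction. That gives 3 × 4 × 2 = 24 profiles, leaving rule 5 aside.

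1. Prior anticoagulant: 2 × 4 × 2 = 16 profiles, under rule 1. Remaining: 24 − 16 = 8.
2. Two or more events: 2 profiles, under rule 2. Remaining: 6.
3. Occlusive: 3 profiles, under rule 4. Remaining: 3, all non-occlusive with no prior anticoagulant.
4. Of these, one event falls under rule 3 on either reading. So does no history with silent thrombosis.
5. The last profile has no events and no silent thrombosis. If fewer than two includes zero, rule 3 applies, and none of the 24 profiles reaches rule 6. If it means exactly one, rule 6 applies, and 1 of 24 reaches it.

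On the numerical reading, then, rule 3's silent-event clause is redundant and rule 6 is empty. On the exactly-one reading, both have a purpose.

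The numerical reading would also place two of the 16 profiles in step 1 (prior user of either class, no events, no silent thrombosis, non-occlusive) under rule 3 as well as rule 1. If rule 3's word for starting treatment is taken to mean patients not already anticoagulated, rule 1 governs them on either reading.

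**Size.** Section 15.1 plans 45 non-thrombotic patients among 170 pivotal patients: 45/170 = 26.5%, given there as approximately 26%. Those already anticoagulated (rule 1) and those with occlusive obstruction (rule 4) must be taken out. The protocol gives neither number, so 26% is a ceiling and not an estimate. A profile count is not a patient count, so 1 of 24 is not an estimate either.

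**The case against.** The strongest reply concerns rule 3. The sentence contrasts a history with no history and uses *event* in the singular. Its natural meaning is exactly one event, with zero-event patients entering only through the silent-event clause. That the numerical reading makes the clause redundant is itself evidence against that reading. This stands: rule 3 is unclear drafting and not a contradiction.

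A reader might infer that 26% of the pivotal patients face conflicting instructions. The documents do not support that, because rules 1 and 4 remove an unstated number of them and the exactly-one reading removes the conflict altogether.

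A reader might also infer that rule 1 collides with rules 3 and 4 wherever they overlap, since neither repeats the exclusion in rule 2. That is too strong. Rule 3 speaks of patients who will begin anticoagulation, which suggests that they are not already on it. Rule 4 accepts either class, so a patient treated as rule 1 says also satisfies rule 4.

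It is fair to add that the rules are called guidelines, that treatment for concomitant conditions is left to the physician, and that no effect on patency or bleeding has been quantified. Appendix 2 may resolve these points in practice; its absence from the available text is not a defect of the plan. If it does resolve them, sites may already be acting consistently. The body text of rule 1 would still need correction, because the mismatch lies within the rule itself.

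**Conclusion.** Rule 1 is wrong as written. It is an internal inconsistency and not a disputed design choice, and it affects every patient who enters on a direct thrombin or Factor Xa inhibitor, a number that the protocol does not state. This holds whichever way rule 3 is read.

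The rule 3 point is secondary and amounts to ambiguity. It makes a difference only for patients with no prior anticoagulant, no events, no silent thrombosis and non-occlusive obstruction, an unstated share that comes mainly from the non-thrombotic stratum and is bounded above by that stratum's 45 of 170. This narrowing sets aside the clopidogrel/prasugrel rule and assumes that rule 3 addresses patients not already anticoagulated.

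Neither point alters the sample size, the hypotheses or the test statistic. The consequence is possible variation in treatment between sites, relevant to patient safety and to the thrombosis component of the primary endpoint. Its size cannot be derived from the documents.

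**What to change.** The sponsor's clinical team should:

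- reconcile rule 1 so that the drug class it names matches the patients it covers;
- state whether fewer than two prior events includes patients with no events;
- confirm that each patient falls under one rule, and that Section 9.5.3 and Appendix 2 agree.

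Which regimen applies to whom is for that team to decide, and none is suggested here. No further data collection is asked for: the schedule in Section 10 already records the anticoagulation regimen at implant, discharge, 1, 6 and 12 months and at interval evaluations. The cost is a wording clarification in the protocol and a notice to sites.

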9.6 Discharge or Three Days Post-Procedure (whichever comes first)

- Duplex ultrasound to determine post-procedural target vessel lumen diameter (For patients refusing the venographic assessment at 12 months [or prior Interval Evaluation, as applicable], DUS-determined patency will be used instead, with the DUS obtained at the Discharge or Three Days Post-Procedure visit serving as the baseline).
- Determination of discharge
- Anticoagulation Review, based on the Extended Anticoagulation Protocol (See Appendix 2.)
- Adverse event assessment
- Patients who do not meet intra-procedural inclusion criteria (and who do not receive the implanted study device) should be followed only through hospital discharge for protocol deviations and adverse events. This visit will conclude participation for these screen failed patients. These subjects will not be included in the statistical analysis.

9.7 1 Month Evaluation (30 days -7/+14 days)

- Physical examination (to assess for the presence of Adverse Events)
- Anticoagulation Review, based on the Extended Anticoagulation Protocol (See Appendix 2.)

9.8 6 Month Evaluation (180 days ± 30 days)

- Physical examination (to assess for the presence of Adverse Events)
- Duplex ultrasound (required only for first 30 patients to assess patency)
- CIVIQ-2 Quality of Life questionnaire (See Appendix 5.)
- VAS pain score
- VCSS (See Appendix 7.)
- Anticoagulation Review, based on the Extended Anticoagulation Protocol (See Appendix 2.)

9.9 12 Month Evaluation (365 days ± 60 days)

Patients that refuse the venogram and IVUS at this visit should have all other assessments listed here performed:

- Physical examination (to assess for the presence of Adverse Events)
- Assessment of primary patency by venography

STE-HUM-007P US Clinical Protocol Revision C

- Determination of residual external venous segment compression, stent recoil, and lesion coverage by IVUS
- Duplex ultrasound for all patients (For patients refusing the venographic assessment at this visit, DUS-determined patency will be used towards the primary efficacy endpoint instead.)
- Assessment of stent integrity by bi-plane X-Ray (See Appendix 3.)
- CIVIQ-2 Quality of Life questionnaire (See Appendix 5.)
- VAS pain score (See Appendix 6.)
- VCSS (See Appendix 7.)
- Anticoagulation Review, based on the Extended Anticoagulation Protocol (See Appendix 2.)

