- 16. Known hypersensitivity to nickel or titanium
- 17. Contrast agent allergy that cannot be managed adequately with pre-medication
- Intended concurrent thrombolysis or thrombectomy procedure OR intended or planned (within 30 days) adjuvant procedure such as creation of temporary AV fistula, placement of IVC filter, endovenectomy or saphenous vein ablation
- 19. Current or recent (within 30 days) active participation in another drug or device clinical trial (Participation in observational studies is acceptable.)
- 20. Patient judged to be a poor candidate by the primary investigator
- 21. Patients who have had any prior surgical or endovascular intervention of the target vessel Note: Patients who have had catheter-directed or mechanical thrombolysis in the target vessel for DVT at least 3 month (90 days) prior to the VIRTUS index procedure may be included in the trial.
- 8.2.3 Exclusion Criteria Intra-procedural Criteria
 - 22. Patients in whom the lesions cannot be traversed with a guide wire. These patients will not count against the study sample size.
 - 23. Patients where the obstruction extends into the inferior vena cava or below the level of the lesser trochanter. These patients will not count against the study sample size.
 - 24. Patients whose vein diameters are not within limits stated in current Instructions for Use as determined by venogram. These patients will not count against the study sample size.
 - 25. Patients who do not meet the venogram binary stenosis definition above, as determined by the treating physician. These patients will not count against the study sample size.

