9.2 Informed Consent

All patients who meet the pre-procedural inclusion criteria will have the study presented to them, as well as their family if possible. Patients must document consent to the study by signing the approved consent form. One copy of the informed consent will be placed in the patient's medical record, a second will be given to the patient or representative, and a third may be placed in the study records.

Patients that sign the informed consent will be considered enrolled in the study. These patients should also be entered into the electronic data capture (EDC) system and monitored for protocol deviations and adverse events until discharge from the hospital. Subjects that sign consent, but are found to not meet Inclusion/Exclusion criteria (i.e. screen failures) will not be included in the statistical analysis.

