9.5 Venous Stent Implant Procedure

9.5.1 Procedure Guidelines

STE-HUM-007P US Clinical Protocol Revision C

Patients who meet all of the inclusion and exclusion criteria will undergo the venous stenting procedure. During the venous stenting procedure, the current Veniti Vici Venous Stent System Instructions for Use will be followed.

- Patients will be monitored, per local institutional guidelines.
- Patients will receive appropriate sedation and anesthesia, per local institutional guidelines.
- Venography will be performed to determine sizing for venous stenting with the Veniti Vici Venous Stent System and to evaluate lesion characteristics.
- IVUS will be performed to confirm sizing for venous stenting with the Veniti Vici Venous Stenting System. Assessment of target lesion presence/absence, lesion severity (maximal binary stenosis), and lesion characteristics, per the case report form (location, length).
- Occluded veins will require guidewire recanalization before stenting.
- The lesion(s) must be adequately covered by the stent(s).
- If 2 or more stents are required to cover the target lesion, the stents will be overlapped by at least 1 cm to insure adequate stent cover without skipped areas.
- The diameter of the stent should be 2 mm greater than ("over") the measured diameter of the surrounding "normal" vessel. The stent should be at least 1 cm longer than the obstructive venous lesion (0.5 cm (peripherally) and 0.5 cm centrally. When selecting stent length, the expected foreshortening should be taken into account.
- 9.5.2 Perioperative Anticoagulation Regimen
 - Patients on long-term warfarin therapy should be bridged prior to the intervention with LMWH or other anticoagulant per local institution guidelines, and will restart warfarin therapy within 24 hours.
 - All patients will receive prophylactic LMWH or other anticoagulant prior to the intervention and following the procedure, per local institutional guidelines.
 - This applies to all patients, including those bridged, as described in Bullet 1 of Section 9.5.2 above.
 - All patients should be appropriately anticoagulated during the procedure, per hospital protocol.
 - SCD compression/early ambulation post-intervention will occur in all patients.

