11.1.4 Major Adverse Event (MAE)

All **major adverse events (MAEs)** must be reported within 24 hours of knowledge of the event to the Sponsor or Sponsor Designee. A subcategory of SAEs include any of the following primary safety endpoints occurring within 30 days of the study procedure:

- Device or procedure-related death
- Device or procedure-related bleeding at the target vessel and/or the target lesion or at the access site requiring surgical or endovascular intervention or blood transfusion ≥2 units
- Device or procedure-related arterial or venous injury occurring in the target vessel segment and/or target lesion location or at the access site requiring surgical or endovascular intervention
- Device or procedure related acute DVT outside of the target vein segment
- Clinically significant pulmonary embolism defined as being symptomatic with chest pain, hemoptysis, dyspnea, hypoxia etc... AND be documented on CT
- Embolization of stent

These events may also need to be reported per requirements of the reviewing EC.

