Hematoma: Localized mass of extravasated blood \geq 5 cm that prolongs hospitalization.

Hemorrhage: Bleeding requiring hospitalization, repeat procedure, operation or transfusion.

Hypertension: Increase in systolic blood pressure above 140 mm Hg or a diastolic blood pressure above 90 mm Hg.

Hypotension: Fall in systolic blood pressure that requires intravenous treatment with vasopressors or inotropic agents.

lliofemoral DVT: DVT involving complete or partial thrombosis of the iliac vein or the common femoral vein, or both, with or without femoropopliteal DVT.

Index Procedure: The procedure in which the subject has the study procedure performed or attempted.

Infection: Inflammation caused by bacterial or viral sources, such as, urinary tract infection, puncture site infection, sepsis, endocarditis, and bacteremia from IV site.

Inflammation: An immunologic response to infection or trauma that can result in localized redness, swelling, heat, pain and dysfunction of the organs involved.

Invasive Assessment/Procedure: Any assessment, intervention or therapy that penetrates the skin, excluding administration of parenteral fluids or drugs.

Kidney Failure: Failure of the kidneys to perform essential functions that requires dialysis.

Myocardial Infarction (Non-Q wave): Post-treatment elevation of CK-MB more than 3 times the upper limit of lab normal value without evidence of pathologic Q-waves present on EKG. Elevated serum troponin levels are not sufficiently validated to be considered sole evidence of an MI in the absence of CK-MB elevations.

Myocardial Infarction (Q wave): Development/appearance of new pathological Q-waves in more than 2 contiguous leads per 12-lead electrocardiogram (EKG/ECG).

Peripheral: refers to a location away from the heart; retrograde to the flow

Physician-Directed Subject Withdrawal: Withdrawal of a subject from the study at the direction of the Principal Investigator. Reasons for physician-directed subject withdrawal include, but are not exclusive to: the subject is not adhering to the Study Protocol requirements, the subject has enrolled in another study that conflicts with the VIRTUS outcomes of interest, or the physician deems it in the best interest for the safety or welfare of the subject to withdraw.

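### The 30-day safety rate covers implanted patients only: patients with a failed crossing attempt are left out of the analysis and followed only to discharge

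*Combined protocol and SAP*

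**What the plan says.** Section 9.2 fixes enrolment at consent: "Patients that sign the informed consent will be considered enrolled in the study". It then removes screen failures: "Subjects that sign consent, but are found to not meet Inclusion/Exclusion criteria (i.e. screen failures) will not be included in the statistical analysis".

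Section 8.2.3 lists four intra-procedural exclusions (22 to 25): a lesion that a wire cannot cross, obstruction outside the permitted segment, vein diameter outside the Instructions for Use, and stenosis below the venographic threshold. Exclusion 22 reads: "Patients in whom the lesions cannot be traversed with a guide wire. These patients will not count against the study sample size".

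Under Section 9.6, patients who fail at this stage and receive no device "should be followed only through hospital discharge for protocol deviations and adverse events", and "These subjects will not be included in the statistical analysis".

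Three other places bear on this:

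- Section 9.5.1, within the implant procedure: "Occluded veins will require guidewire recanalization before stenting".
- Section 11.1.4, the primary safety composite, which runs to 30 days after the study procedure. One component is "Device or procedure-related arterial or venous injury occurring in the target vessel segment" or at the access site, if it needs surgical or endovascular intervention.
- Appendix 4, defining the index procedure: "The procedure in which the subject has the study procedure performed or attempted".

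**The concern.** A crossing failure is known only after access has been obtained and a wire has been worked against the lesion. By then the patient has been exposed to the access bleeding, vessel injury and thrombosis that the composite is meant to count. If the attempt fails, the patient is reclassified as a screen failure and leaves both numerator and denominator. Unlike an ordinary screening exclusion, this one depends on how the intervention went.

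What is at stake is the meaning of the reported safety figure. A patient offered the procedure accepts the risk of the attempt. The planned rate gives the 30-day risk among patients in whom a stent was placed. Events between discharge and day 30 in the others would be hard to recover later, because their participation has ended.

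**Working it through.** **1. The composite against the exclusion.** Section 11.1.4 has six components. Five can occur without an implant: related death, related bleeding, related arterial or venous injury, related DVT outside the target segment, and symptomatic pulmonary embolism. Only stent embolization needs a stent. The window is 30 days, while Section 9.6 stops at discharge. No section defines a safety population of attempted procedures. Section 9.10 says all patients complete the 30-day safety assessment; in context this probably means implanted patients, but it does not say so. Because the exclusion is general, it also removes crossing failures from the denominators of technical, lesion and procedural success in Section 15.9.1.

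**2. The plan's own figure.** Inputs from Section 15.7.1: freedom-from-event goal 0.94 (event rate 0.06), one-sided exact binomial test at 0.025, about 170 subjects, expected MAE rate 1%.

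- P(Y ≤ 4 | 170, 0.06) = 0.0226, and P(Y ≤ 5 | 170, 0.06) = 0.0545. The test passes with at most 4 MAEs.
- Power = P(Y ≤ 4 | 170, 0.01) = 0.971. The stated power above 90% is reproduced.

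**3. Assumptions for the patients left out.** The documents give neither the number of failed attempts nor their MAE risk. I take k = 4 to 9 added to 170 (4/174 = 2.3%; 9/179 = 5.0%) and a risk m of 1%, 5% or 10%. As a wider case, Section 4.2 cites technical success above 90%, which suggests a ceiling near 10%, or k = 19 (19/189 = 10.1%).

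**4. Pass limit after adding them.** It stays at 4 MAEs throughout.

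| N | p with 4 MAEs | p with 5 MAEs |
|---|---|---|
| 174 | 0.019 | 0.047 |
| 179 | 0.016 | 0.039 |
| 189 | 0.010 | 0.027 |

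**5. Chance that a pass would become a fail.** Let Y be MAEs in the 170 implanted patients (rate 1%) and X those in the k added patients (rate m). Since the limit does not move,

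P(reversal) = P(Y ≤ 4) − P(X + Y ≤ 4) = Σ P(Y = y) · P(X ≥ 5 − y), y = 0 to 4.

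Example, k = 4, m = 5%: 0.0633 × 0.1855 (y = 4) + 0.1502 × 0.0140 (y = 3) + about 0.0001 (y = 2) = 0.014.

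Example, k = 9, m = 10%: 0.9711 − 0.8817 = 0.0894.

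| k | m = 1% | m = 5% | m = 10% |
|---|---|---|---|
| 4 | 0.3% | 1.4% | 3.1% |
| 9 | 0.6% | 3.7% | 8.9% |
| 19 | 1.4% | 9.8% | 26% |

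At m = 20% the range for k = 4 to 9 is 7% to 24%.

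**The case against.** The strongest reply is that the rule is explicit and deliberate. Sections 15.7.1 and 15.8.2 frame the safety hypothesis around use of the stent, and a patient whose lesion is never crossed does not receive one. Section 11.1.4 ties the window to the study procedure, not to the index procedure, so the Appendix 4 definition supports the concern but does not by itself create a contradiction. Adverse events of these patients are entered and monitored until discharge, which covers immediate access bleeding and many injuries, and the DSMB reviews all safety data. All of this stands. It justifies keeping the implanted set for the formal test. It does not explain why a composite that counts procedure-related harm to day 30 has no table for failed attempts and no day-30 status for them.

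Three stronger readings are tempting, and the documents do not support them:

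- *One excluded injury would overturn the safety finding.* A single extra event does so only if there are exactly 4 MAEs among the 170. At the plan's expected 1% rate that has probability 0.063.
- *The analysed set is successful procedures.* It is implanted patients. Those with residual stenosis, skipped segments, non-study devices or an embolized stent remain in it.
- *The rule removes the cases where injury is most likely.* Nothing in the documents gives the injury risk of failed crossings. The series of 953 limbs cited in Section 4.2 covers stented limbs only.

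The exclusion is also broader than crossing failure. Exclusions 23 to 25 can be met on diagnostic venography with no crossing attempted, so a supportive set must say who belongs in it.

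**Conclusion.** The concern holds as one of coverage and reporting. As written, the 30-day MAE rate describes implanted patients. Harms of a failed crossing attempt are recorded to discharge but not analysed, and those from discharge to day 30 are not collected.

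The likely effect on the formal test is small: roughly 0.3% to 9% for 4 to 9 failed attempts with an MAE risk of 1% to 10%, given a 1% rate in implanted patients. It becomes material only with more failures or a much higher risk. These figures show how far the conclusion could depend on the excluded patients. They are not an effect of the proposed change, which leaves the formal test alone.

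**What to change.** 1. Keep the implanted set for the formal safety test and say so explicitly.
2. Reconcile Sections 8.2.3, 9.2, 9.6, 9.10 and 11.1.4 and the Appendix 4 definition, so that they agree on which patients the 30-day assessment and the MAE count cover. Section 9.6 also refers to intra-procedural inclusion criteria, although Section 8.2.3 lists only exclusions.
3. Prespecify a supportive table of CEC-adjudicated MAEs, with an exact confidence interval, for all patients in whom venous access was obtained and lesion crossing was attempted. Show non-implanted patients separately, and list apart those excluded on diagnostic venography alone.
4. Obtain one 30-day telephone contact for patients attempted but not implanted.

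The cost is one table, a few calls, and a supportive rate that may look slightly less favourable.
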